a) Page 22, third paragraph, starting with first sentence: Currently, no licensed vaccine against RSV is available, although there is broad consensus that such a vaccine is urgently needed and should be a global health priority to protect healthy older infants and toddlers. Although passive immunoprophylaxis with the RSV-neutralizing monoclonal antibody palivizumab (Synagis®; MedImmune) is available for high-risk infants, this approach is not feasible for general use. In addition, in August 2023, the Centers for Disease Control and Prevention (CDC) director adopted the recommendation from the CDC Advisory Committee on Immunization Practices (ACIP) to approve nirsevimab (1). Nirsevimab is an FDA-licensed monoclonal antibody active against RSV to provide passive immunity to healthy infants up to eight months old during their first RSV season and to high-risk children eight to 19 months during their second RSV season (2). Additionally, on 21 August 2023, licensure of the RSVpreF maternal vaccine was approved for use at 32 through 36 weeks gestational age of pregnancy (3). While both products are expected to provide passive immunity to younger infants, they do not provide active, durable immunity and are not expected to protect healthy older infants and toddlers against RSV disease. Pursuit of vaccines for active immunization against RSV is important because protection from passive antibodies (from either nirsevimab or maternal immunization) is short-lived- lasting no more than 6 months. There is significant burden of RSV disease in children who are older than eight months of age during RSV season who will not be recommended to receive nirsevimab. For example, globally, the incidence in 6-12 months-old children of RSV lower respiratory illness is estimated at 82 per 1000 per year, with an estimated 4.1 to 8 million episodes annually in this age group, resulting in a rate of hospitalization of about 1% annually (estimated numbers: 500,000 – 970,000 hospital admissions) (4), In the United States, for children from 7 to 20 months of age, rates of inpatient RSV infections were ~3 per 1000, emergency room RSV \sim 30 per 1000, and outpatient visits \sim 60 per 1000 (5, 6). In contrast to the passive immunity provided by nirsevimab or maternal RSV preF, live-attenuated vaccines studied in this protocol prime the infants' immune system and induce active RSV immunity, which should provide long-lasting immunity with potent memory responses. [...]

- 4. Section 4.2, Exclusion Criteria
 - a) 4.2.6, Page 38: Previous enrollment in this trial, previous maternal or pediatric receipt of a licensed or investigational RSV vaccine, or previous maternal or pediatric receipt of or planned administration of any other anti-RSV product (such as ribavirin or RSV IG or RSV mAb) within four months of screening or planned administration of an anti-RSV product between screening and day 56 after enrollment.
- 5. Section 5.11, Concomitant Medications
 - a) 5.11.2, Precautionary Concomitant Medications, Page 46, new bullet point:

Due to their potentially confounding effect on immunogenicity results, the following treatments should be avoided after study product administration unless clinically indicated:

- Systemic corticosteroids for more than 14 days at a dosage equivalent to prednisone at >2 mg/kg or 20 mg daily or other immune-modifying drugs
- Immunoglobulins and/or any blood products
- Anti-RSV products (such as ribavirin or RSV IG or RSV mAb)
- 6. Section 7.2, Safety-Related Data Collection
 - a) Laboratory Test Results, Page 62, Table 5: AE eCRF Entry Requirements, Row Throughout Study, Column Concomitant Medications to enter into eCRFs:

Study Phase at the time of event onset	Calendar Date	AEs to enter into eCRFs	Concomitant Medications to enter into eCRFs
Throughout study	ANY	 Updated data on unresolved AEs or serious AEs with onset date during the timeframe from study product administration (Day 0) to midnight on the 28th day after Day 0 Updated data on unresolved serious AEs with onset date prior to midnight on the 56th day following Day 0 Updated data on unresolved serious AEs with onset date during RSV Surveillance Period or related to the Post-RSV Season Study Visit Note: unresolved events should be followed to resolution or until no further change is expected. 	 All concomitant medications administered to treat the entered event All prohibited and precautionary medications (see Section 5.11)

Informed Consent Forms

- 7. Appendix VI, Informed Consent Form for Study Participation
 - a) Key Information, Page 96, last bullet: You may choose to not allow your child to take part in this study. Two products have been developed to protect young infants against RSV disease.

However, Tthere are is currently no licensed vaccines to protect against RSV illness product available to provide long-lasting protection against RSV disease to healthy older infants and children.

# **Version History**

1.1 U	Original Version  Updated with protocol LoA #1  Revised footnote for Appendix 1  Clarify that we will use Wilcoxon signed-rank tests for pair-wise comparisons rather than Wilcoxon rank sum tests (Section 4.3.1)  Update Attachment 1: Writing team roster	08MAY2019 10MAR2020
( )	Revised footnote for Appendix 1  Clarify that we will use Wilcoxon signed-rank tests for pair-wise comparisons rather than Wilcoxon rank sum tests (Section 4.3.1)	10MAR2020
2.0	
 
Clarified that the window for Post-RSV season visits may be extended to September 30 due to operational interruptions related to COVID-19.
 
Updated text to indicate that Illness Visit specimens may be collected by either nasal wash (if Illness Visit prior to COVID-19 pandemic) or nasal swab (if Illness Visit after COVID-19 pandemic).
 
Updated text regarding sample size and study design indicating RSV 276 arm was closed.
 
Removed the specification that viral vaccine will be isolated by culture for Go/No-Go Criteria #3. Quantitation will now be based primarily on PCR, as viral culture will not be reliable on samples collected by parents/guardians.
 
Further clarified that we will use Wilcoxon signed-rank tests for paired comparisons between time points and pair-wise Wilcoxon rank sum tests for comparisons between arms. (Section 4.3.1).
 
Added additional analyses for primary and secondary objectives to examine seasonal effects and account for potential ascertainment differences related to COVID-19.
 
Updated Attachment 1: Writing team roster.
 
	02SEP2021

3.0	Updated with protocol version 3.0	14JUN2022
	Clarified that the RSV season surveillance period starts in the calendar year of the participant's study product administration.	
	
 
Clarified that the Post-RSV visit is to occur between April 1 - April 30 in the calendar year following study product administration.
 
	
	Updated language to further clarify when the go/no-go assessment would be assessed.	
	Clarified language regarding children from the same household. For immunogenicity analyses, one participant will be randomly selected to be included in the primary analysis if two or more participants are enrolled from the same household on the same date. Also updated conditions for enrollment of multiple children from same household.	
	Updated Attachment 1: Writing team roster.	
4.0	
 
Updated with clarification memo #1 to protocol version 3.0
 
Updated go/no-go criteria from RSV neutralizing antibody to IgG antibody to RSV F protein
 
Added bronchiolitis to the list of solicited adverse events
 
Removed language specifying RSV virus (wt or vaccine virus) corresponding to Illness Visits would only be detected by "immunoplaque assay".
 
Revised text to indicate that tests for homogeneity will be based on Breslow-Day test.
 
	10MAR2023
5.0	
 
Updated with letter of amendment #1 to protocol version 3.0
 
Clarified that participants who receive concomitant medications that may confound results will be excluded from the immunogenicity analysis population and virology-based analyses.
 
Updated Attachment 1: Writing team roster.
 
	07NOV2023

### 1 Introduction

## 1.1 Purpose

This Primary Statistical Analysis Plan (SAP) describes analyses of the primary and secondary outcome measures of IMPAACT 2021 which address the primary and secondary objectives of the study. The Primary SAP outlines the general statistical approaches that will be used in the analysis of the study. It has been developed to facilitate discussion of the statistical analysis components among the study team, and to provide agreement between the study team and statisticians regarding the statistical analyses to be performed and presented in the primary analysis report. It also describes the results for the primary and secondary outcome measures that will be posted on ClinicalTrials.gov.

Detailed outlines of tables, figures, and coding descriptions that will be included in the Primary Analysis Report are included in the Analysis Implementation Plan (AIP). Analyses for the Primary Statistical Analysis Report will be initiated once the last participant has completed their Day 56 follow-up visit and associated immunologic and virologic data are in the study database, all queries have been resolved, and the database frozen for analysis. As this study has extended follow-up beyond the primary completion date, an additional statistical analysis report addressing the remaining objectives will be initiated once the last participant has completed their Post-RSV Season Visit and all virology data are in the study database, all queries have been resolved, and the database frozen for analysis. Outlines of analyses for exploratory objectives and outcome measures not included in the Primary SAP will be provided in a separate SAP for Other Objectives.

## 2 Study Overview

#### 2.1 Study Design

IMPAACT 2021 is a multi-center, Phase I/II, double-blind, randomized, placebo-controlled study to assess the safety and immunogenicity of three Respiratory Syncytial Virus (RSV) vaccine candidates (RSV ΔNS2/Δ1313/I1314L, RSV 6120/ΔNS2/1030s and RSV 276) in RSV-seronegative children, and to determine whether any vaccines are good candidates to move forward into larger efficacy studies. Under protocol V2.0, participants will be randomized equally to receive RSV ΔNS2/Δ1313/I1314L vaccine, RSV 6120/ΔNS2/1030s vaccine, or placebo (a third vaccine, RSV 276, was previously included under protocol V1.0; no participants will receive this vaccine under protocol V2.0). Approximately 130 healthy RSV-seronegative children 6 to <25 months of age will be randomized, including approximately 40 each in the placebo and two candidate vaccine arms that remain open under protocol V2.0, as well as all participants previously randomized to receive RSV 276 under protocol V1.0 prior to closure of this arm.

Eligible children from the same household are allowed to enroll: they must either be enrolled on the same date and to the same study arm or additional children in the household can be enrolled and randomized independently after other children in the household complete the Day 56 Visit. Enrollment will take place outside the time during which wt RSV circulates in the community at each site. RSV circulation will be determined by the Protocol Team through local and national surveillance and communication with the study sites, with additional guidance provided in the Manual of Procedures (MOP)). Children will remain on study until they complete the Post-RSV Season Visit between April 1 – April 30 in the calendar year following study product administration; however, this window may be extended to September 30 if sites experience operational disruptions due to COVID-19). Expected length of follow-up for a given participant is between 4 and 15 months depending on time of enrollment.

#### 2.2 Hypotheses

The live-attenuated RSV vaccine candidates RSV ΔNS2/Δ1313/I1314L, RSV 6120/ΔNS2/1030s, and RSV 276 will each be safe and immunogenic in RSV-seronegative recipients. However, these vaccine candidates may have safety signals that become apparent only when analyzed in a larger number of participants, and the candidates may differ in the magnitude and longevity of antibody responses, and in responses observed following naturally occurring RSV infection. To move forward, the vaccines should:

- be safe, and
- result in at least 70% of the population of vaccine recipients having a ≥4-fold rise in serum RSVneutralizing antibody titers from pre-study product administration to the Day 56 Visit after study product administration

#### 2.3 Study Objectives

This Primary SAP addresses the following primary and secondary objectives listed in the study protocol. Other study objectives in the protocol will be addressed in subsequent analysis plans.

#### 2.3.1 Primary Objectives

- Safety: To estimate and compare (each vaccine group to placebo) the frequency and severity of adverse events (AEs) following study product administration (Day 0) through Day 56
- Immunogenicity: To estimate and compare (between the vaccine groups and to the benchmark of 70%) the percentage of vaccinees having a ≥4-fold rise in serum RSV-neutralizing antibodies at the Day 56 Visit

#### 2.3.2 Secondary Objectives

- Immunogenicity: To estimate and compare (between the vaccine groups) the percentage of vaccinees with a ≥4-fold rise in serum IgG antibody to RSV F protein (RSV F IgG) at the Day 56 Visit
- Immunogenicity: To estimate and compare (between the vaccine groups) the titers of serum RSV
   F IgG and serum RSV-neutralizing antibodies at the Day 56 Visit
- Safety: To describe and compare the frequency and severity of RSV-associated medically attended acute respiratory illness (RSV-MAARI) and RSV-associated medically attended acute lower respiratory illness (RSV-MAALRI) in the placebo and vaccine arms during RSV season

#### 2.4 Overview of Sample Size Considerations

The target sample size of approximately 40 per arm was chosen to gather more data on safety and to yield sufficiently precise confidence intervals around Day 56 immunogenicity to help inform which candidate vaccines should go forward into larger studies. The total expected sample size is approximately 130, including approximately 40 each in the placebo and two candidate vaccine arms that remain open under protocol V2.0 (RSV ΔNS2/Δ1313/I1314L, RSV 6120/ΔNS2/1030s), as well as all participants previously randomized to receive RSV 276 under protocol V1.0 prior to closure of this arm.

To fully assess safety, much larger sample sizes will be required, and additional studies will need to be conducted on the candidate vaccines identified as promising in this trial. Declaring superiority in immunogenicity of one vaccine candidate over another will only be possible if one candidate has very poor immunogenicity. Additional details regarding sample size considerations are included in Section 9.3 of the protocol.

#### 2.5 Overview of Formal Interim Monitoring

The NIAID Intramural Data and Safety Monitoring Board (DSMB) will provide independent oversight to safeguard the well-being of study participants and to monitor study integrity. The DSMB will meet biannually to monitor participant safety with regard to adverse events and efficacy; to review analyses outlined in the statistical section of the protocol; and to discuss problems regarding accrual, study compliance, data quality and completeness.

If IMPAACT 2021 is not fully accrued at the end of an enrollment season and an additional enrollment season is considered, the DSMB will review unblinded data to determine if all candidate vaccines should remain in the study. The DSMB will use the following Go / No-Go criteria as specified in the protocol as guidance in making that decision.

	Yes	No
1. Is there a statistically significant (p<0.05) difference in the percentage with immune response (e.g., ≥4-fold rise in serum IgG antibody to RSV F protein) to the candidate vaccines such that one or two products can be identified to be immunologically superior to the remaining product or products, with the absence of a safety signal among the higher performing product(s)?		
If yes, the DSMB may recommend that the study close to acc	rual	
If no, the DSMB will consider the following questions for each	specific product	:
2. Is the upper limit of the 95% confidence interval for the percentage of participants exhibiting immune response (e.g., ≥4-fold rise in serum IgG antibody to RSV F protein) at the Day 56 Visit less than 70%?		
3. Have more than two participants receiving the specific product experienced lower respiratory illness (LRI) of ≥ Grade 2 in the 28 days following study product administration for which vaccine virus was isolated without other potential explanation?		

4. Were there two or more participants who experienced vaccineassociated Grade 4 events of similar type (as listed below) after study product administration with presence of vaccine virus without other potential explanation? Otitis media within 28 days of study product administration

Pharyngitis within 28 days of study product administration

#### 3 **Outcome Measures**

#### 3.1 **Primary Outcome Measures**

Safety Outcome measures:

- Grade 1 or higher solicited AEs as defined in Appendix 1 from Day 0 through Day 28
- Grade 2 or higher LRIs as defined in Appendix 1 from Day 0 through Day 28
- Serious AEs as defined in Appendix 4 from Day 0 through Day 56

Additional grading criteria are included in Appendix 2 and 3.

Immunogenicity Outcome measure:

≥4-fold rise in serum RSV-neutralizing antibody titer from pre-study product administration (screening) to the Day 56 Visit

#### 3.2 **Secondary Outcome Measures**

Immunogenicity Outcome measure [Secondary Objective 1]:

≥4-fold rise in serum RSV F IgG from pre-study product administration (screening) to the Day 56 Visit

Immunogenicity Outcome measures [Secondary Objective 2]:

- Titer of serum RSV F IgG at the Day 56 Visit
- Titer of serum RSV-neutralizing antibodies at the Day 56 Visit

Safety Outcome measures [Secondary Objective 3]:

- RSV-MAARI and maximum grade (if more than one illness within a participant)
- RSV-MAALRI and maximum grade (if more than one illness within a participant)

# 4 Statistical Principles

#### 4.1 General Considerations

#### 4.1.1 Analysis populations

- Any participants found to be ineligible will be included in screening, accrual and eligibility summaries only.
- Safety population: All children (regardless of the number of children enrolled in a given household on the same date) who receive study product will be included in safety analyses. Safety outcome measures will be included if they occur after study product administration.
- Immunogenicity population: Children who received study vaccine and who have available data
  regarding outcome measures at screening and Day 56. If more than one child from a
  household is enrolled on the same date, one participant will be randomly selected to be
  included in the primary analysis.
  - Participants who have received the following treatments prior to the Day 56 visit will be excluded from the immunogenicity population (See Section 5.11.2 of the protocol for additional details):
    - systemic corticosteroids for more than 14 days at a dosage equivalent to prednisone at >2 mg/kg or 20 mg daily or other immune-modifying drugs;
    - immunoglobulins and/or any blood products;
    - anti-RSV products (such as ribavirin or RSV IG or RSV mAb).

#### 4.1.2 Key Definitions

- "Pre-study product administration"
  - At screening, a blood draw is performed for RSV serum antibody testing. The
    measurement corresponding to this blood draw is referred to as the "pre-study product
    administration" measurement.
- "Day 0"
  - The date of study product administration. Study product administration must occur within 42 days of collection of the screening sampling and ideally on the same day as randomization, or, if needed, up to 5 days after randomization.
- "Baseline"

Baseline summaries will use the last evaluation on or before the date of study product administration (Day 0).

- Lower (LRI) and Upper (URI) respiratory illness
  - Solicited adverse events include fever, acute otitis media, LRIs (identified by wheezing, pneumonia, croup, rhonchi or rales), and URIs (identified by rhinorrhea, pharyngitis, cough without LRI and hoarseness), each defined in Appendix 1 of this document. URIs and LRIs are counted as having occurred if any of their associated signs, symptoms or diagnoses are reported.

#### 4.1.3 Analysis windows

• There are three time periods of interest (Acute, Post-Acute, and RSV Season Surveillance). For the purposes of analysis, data included are from:

- Acute Phase: Day 0 28
  - The Acute Phase begins with study product administration (Day 0) and ends at midnight on the 28th day after study product administration.
- Post-Acute Phase: Day 29 56
  - The Post-Acute Phase begins at 12:01 am on the 29th day after study product administration and ends at midnight on the 56th day after study product administration.
- RSV Season Surveillance: Nov 1 to March 31 or as specified in MOP
  - This period starts in the calendar year of the participant's study product administration.
- Post-RSV Season Visits: April 1-30
  - Visits are to occur in the calendar year following study product administration.
  - The allowable window for Post-RSV Season Visits may be extended to September 30 if sites experience operational disruptions due to COVID-19.
- Other: after Day 56 and before November 1
- It is possible for the Acute or Post-Acute Phase and the RSV Season Surveillance period to
  overlap. If participants are enrolled fewer than 56 days before the start of the RSV Season
  Surveillance period, reportable events occurring before Day 56 (possibly during the RSV
  Season Surveillance period) will be included in Acute/Post-Acute summaries rather than the
  RSV Season Surveillance period (unless otherwise specified, see 4.3.2).

#### 4.1.4 Variable summaries

- Baseline characteristics will be summarized by arm, but with no statistical comparisons comparing arms because of the randomized study design.
- Significance levels p < 0.05 will be highlighted in the text, but must be interpreted with caution since there will be many statistical tests and no adjustments for interim monitoring.
- Categorical data will be summarized using N (%), and continuous data using N, min, Q1, median, Q3, max, and mean/geometric mean (standard deviation (SD) or 95% confidence intervals) (when appropriate).
- Any modifications to this statistical analysis plan after the team has seen data that were collected after randomization will be identified as such in the analysis report.

#### 4.2 Analysis Approaches (Primary Objectives)

#### 4.2.1 Analysis of the primary safety objective

There are three primary safety outcome measures (Section 3.1). For each, the number and proportion of participants experiencing at least one primary safety outcome measure in the identified time frames will be summarized by arm with 95% exact confidence intervals (CIs) using the Clopper-Pearson method. Proportions in each vaccine group will be compared to the placebo group using two-tailed Fisher's exact tests with a nominal significance level of 0.05. Differences in proportions between each vaccine arm and the placebo arm will be summarized with 95% CIs.

To account for potential ascertainment differences related to COVID-19, differences in proportions between each vaccine arm and the placebo will be summarized by calendar year of enrollment. A Breslow-Day test with a nominal significance level of 0.05 will be used to test for homogeneity in the vaccine effect by calendar year for each comparison between arms. Unless the Breslow-Day test indicates there is not homogeneity in vaccine effect by calendar year, a strata-adjusted difference in proportions will be summarized using a Cochran-Mantel-Haenszel method with 95% Klingenberg (2014) confidence limits.

In addition, for each primary safety outcome measure, the worst (highest) grade experienced by each participant will be summarized. The severity of solicited AEs from Days 0-28, unsolicited AEs from Days 0-28, and serious AEs from Days 0-56 will be summarized by category and by MedDRA Preferred Term (PT). The worst (highest) adverse event grade within each PT is counted for each participant. Rare events (LRIs and serious AEs) will be listed with details including site-assessed relationship with the study product.

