#### 4.2.2 Analysis of the primary immunogenicity objectives

Children will be classified as a responder to the vaccine if they achieve a ≥4-fold increase in serum RSV-neutralizing antibody titers from pre-study product administration to the Day 56 Visit. Proportions (95% CIs) of responders will be summarized by arm. Each confidence interval will be assessed to determine if the upper limit is less than 70%. Differences between each vaccine arm and the placebo arm (which take into account background rates which could vary by season), as well as differences between each combination of vaccine arms, will be summarized with 95% CIs. Pair-wise differences in response rates between the vaccine arms (and differences between vaccine and placebo arms) will be assessed using two-tailed Fisher's exact tests with a nominal significance level of 0.05.

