### 4.5 Analysis Approaches (Virology)

At each Illness Visit, a respiratory viral sample will be collected (i.e., nasal wash or nasal swab) to evaluate for the presence of RSV and other respiratory pathogens (adventitious agents). Note: Under protocol version 1.0, nasal wash samples were collected from participants. Under protocol version 2.0, the collection has been changed to nasal swab samples to decrease potential exposure of study staff to SARS-CoV-2 and allow parents/guardians to collect samples, if possible and feasible for parents/guardians. During each study period (Acute Phase, Post-Acute Phase, and RSV Season Surveillance), more than one nasal wash/swab might be performed. The overall number and proportion of children with at least one Illness Visit nasal wash/swab will be calculated for each vaccine arm by study period. Frequencies will also be calculated for each calendar year and collection method (caretaker versus medical personnel).

Among those with respiratory viral sample test results, the number and proportion with each observed combination of vaccine virus RSV, wt-RSV, and other adventitious agents will be calculated by study period and by arm. Among all children, the number and proportion with an Illness Visit where RSV virus (wt or vaccine virus) was detected (with or without other adventitious agents detected) will also be calculated for each vaccine arm by study period. Frequencies will also be calculated for each calendar year and collection method (caretaker versus medical personnel).

Participants who receive the following treatments will be excluded from analyses, unless they experienced an illness visit prior to receiving treatment:

- systemic corticosteroids for more than 14 days at a dosage equivalent to prednisone at >2 mg/kg or 20 mg daily or other immune-modifying drugs;
- immunoglobulins and/or any blood products;
- anti-RSV products (such as ribavirin or RSV IG or RSV mAb).

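### Tests and crude differences for RSV 276 are not limited to children randomized while that arm was open, so they are exposed to calendar-time confounding

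*SAP*

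**What the plan says.** SAP 2.1 describes RSV 276 as follows: "a third vaccine, RSV 276, was previously included under protocol V1.0; no participants will receive this vaccine under protocol V2.0". The Version History entry for SAP 2.0, dated 02SEP2021, reads: "Updated text regarding sample size and study design indicating RSV 276 arm was closed". On size, SAP 2.4 says "The total expected sample size is approximately 130", made up of "approximately 40 each in the placebo and two candidate vaccine arms that remain open under protocol V2.0" together with "all participants previously randomized to receive RSV 276 under protocol V1.0 prior to closure of this arm". RSV 276 also remains in the hypotheses (SAP 2.2).

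The planned comparisons are:

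- **Safety (SAP 4.2.1).** "Proportions in each vaccine group will be compared to the placebo group using two-tailed" Fisher's exact tests at a nominal 0.05, plus differences from placebo with 95% CIs.
- **Neutralizing-antibody response (SAP 4.2.2).** Differences between each vaccine and placebo, "as well as differences between each combination of vaccine arms, will be summarized with 95% CIs", with pairwise Fisher tests.
- **RSV F IgG response and titers (SAP 4.3.1).** Responders are handled by the primary methods. Titers are compared between arms by Wilcoxon rank sum tests.

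None of these sections limits a comparison involving RSV 276 to children randomized at the same time.

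The SAP does address calendar time. Section 4.2.1 adds differences by calendar year of enrollment, a Breslow-Day test and, unless that test shows heterogeneity, a Cochran-Mantel-Haenszel (CMH) year-adjusted difference. Section 4.2.2 plans the same as secondary analysis (iv). Section 4.3.1 adds response rates by year.

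**The concern.** A child randomized after RSV 276 closed could not have received it, so that child is not a randomized control for RSV 276. SAP 4.2.2 presents the vaccine-placebo difference as allowing for background rates that may change with season. That works only if the placebo children lived through the same seasons. SAP 4.1.4 omits baseline tests because the study is randomized, a premise that fails for RSV 276 against a pooled comparator.

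The SAP gives reasons to expect change over time. It anticipates ascertainment differences from COVID-19. Its Version History also records that bronchiolitis joined the solicited adverse events in SAP 4.0 (10MAR2023), after the closure of RSV 276 had been recorded; whether this was applied to earlier children is not stated.

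A time effect could make RSV 276 look less safe, or hide an excess, and it could shift its response or titers relative to another arm. SAP 4.1.4 highlights p-values below 0.05, and SAP 1.1 says primary and secondary results will be posted publicly. A pooled RSV 276 p-value would be read there as randomized evidence.

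**Working it through.** **Inputs from the documents.** Total about 130; three continuing arms of about 40 (SAP 2.4); two-sided Fisher test at 0.05 (SAP 4.2.1). The RSV 276 count is not stated. The remainder is 130 − 3×40 = 10, which is consistent with the stated total but cannot be checked independently.

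**Assumptions.** RSV 276 n = 10. Of 40 placebo children, k = 10 are concurrent (equal V1.0 allocation is assumed; the ratio is not in the supplied text). There is no vaccine effect. The event rate is p1 while RSV 276 was open and p2 afterwards. The documents give no rates.

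**Crude bias.** The expected spurious difference is ((40 − k)/40) × (p1 − p2). For 80% then 50% this is (30/40) × 0.30 = 0.225, or +22.5 points.

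**Fisher rejection.** Exact enumeration with RSV 276 ~ Bin(10, p1) and placebo ~ Bin(10, p1) + Bin(30, p2):

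| p1, then p2 | Expected crude difference | Fisher p<0.05 |
|---|---|---|
| 80%, 80% | 0 | 2.9% |
| 80%, 70% | +7.5 points | 3.8% |
| 80%, 60% | +15 points | 9.3% |
| 80%, 50% | +22.5 points | 18.8% |
| 80%, 40% | +30 points | 33.0% |
| 50%, 80% | −22.5 points | 22.3% |
| 10%, 5% | +3.75 points | 5.7% |

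**Sensitivity of the 80%-then-50% case.** With 5 or 20 concurrent placebo children, rejection is 25.5% or 9.2%. With 5 RSV 276 and 5 concurrent placebo children it is 5.5%; with 15 and 15 it is 18.1%.

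**What the planned adjustment does.** Mantel-Haenszel weights are n1×n0/(n1 + n0) per year. Suppose one year has 10 against 10 at 80%, and two later years have 0 against 15 at 50%. The weights are 100/20 = 5, 0 and 0, so the adjusted difference is 0.8 − 0.8 = 0. The crude difference is 8/10 − 23/40 = 0.225.

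**Concurrent controls only.** With 10 against 10 at 80%, expected bias is 0 and Fisher rejection is 0.8%. The standard error ratio is √(1/10 + 1/10)/√(1/10 + 1/40) = √(0.200/0.125) = 1.265. At a 50% rate the standard error rises from 0.177 to 0.224.

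**The case against.** The strongest reply is that the SAP already handles calendar time. The by-year differences are unconditional, and for safety they sit in the primary analysis section. The year-adjusted estimate gives no weight to years without RSV 276 children. For binary outcomes this largely removes between-year bias, and that part of the objection stands.

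Four gaps remain:

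- The only planned between-arm p-value for these binary outcomes is the unadjusted Fisher one.
- The adjusted estimate depends on Breslow-Day. If RSV 276 enrolled in a single calendar year, only one stratum is informative and homogeneity cannot be tested. Calendar year also does not separate children randomized before and after closure within the same year.
- For neutralizing-antibody response the adjustment is only a secondary analysis.
- The titer tests have no adjustment.

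A reader might infer more than the documents support:

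- **That all comparators were enrolled years later.** They include concurrent V1.0 children. No enrollment or closure dates are given, only SAP version dates.
- **That the specimen change biases the primary outcomes.** SAP 4.5 does say "Under protocol version 1.0, nasal wash samples were collected from participants", with swabs used later. That concerns Illness Visit virology; the primary outcomes are clinical events and a serum response.
- **That RSV-associated medically attended illness would carry a confounded p-value.** SAP 4.3.2 plans no tests for it.

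It is also fair that SAP 4.1.4 urges caution with p-values, that SAP 2.4 expects superiority between vaccines to be shown only if one performs very poorly, and that enrolling seronegative children outside RSV circulation limits background response. The Analysis Implementation Plan and protocol Section 9.3, which might say more, were not available.

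**Conclusion.** The point holds for the headline Fisher tests and crude differences in SAP 4.2.1 and 4.2.2, and for the RSV F IgG responder tests and between-arm titer tests in 4.3.1, wherever RSV 276 is one of the arms. As written, these are not purely randomized comparisons.

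The size is unknown. The rejection rates rest on assumed counts and event rates and were worked for a binary outcome against placebo; nothing was computed for titers. A 10-point drift barely matters (3.8% against 2.9%), whereas a fall of 30 or 40 points matters a great deal.

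It would be too strong to conclude that the primary analysis as a whole is invalid. Assessment against the 70% benchmark is within-arm and unaffected, as are comparisons among the three arms that stayed open. The by-year analyses would expose much of the problem for binary outcomes. This is a should-fix.

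**What to change.** In SAP 4.2.1, 4.2.2 and 4.3.1, state that every test and difference involving RSV 276 uses only participants randomized while the RSV 276 arm was open. Report the number of RSV 276 children and of concurrent children in each comparator arm. Label any pooled RSV 276 comparison as descriptive and non-concurrent. In 4.3.2, where no tests are planned, show RSV 276 beside its concurrent placebo children. Keep all placebo children for the two continuing vaccines.

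The change is SAP wording only. The price is precision: under the assumed counts, standard errors for RSV 276 differences are about 26% larger (10 against 10 instead of 10 against 40). Results for the other arms do not change. Because this would be a late change, SAP 4.1.4 requires it to be identified in the report if the team has already seen post-randomization data.
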